flexion-extension radiographs will be obtained pre-operatively on all patients and at one year after surgery to assess cervical fusion and/ or radiographic complications. Standing cervical-thoracic-lumbar-sacral films will be obtained on all patients pre-operatively and at one year postoperatively (post-operatively in the randomized group only) to assess cervical as well as overall sagittal balance. A cervical spine CT will be obtained on patients at 1 year who have an NDI score > 30 or whose plain films suggest instability.

7) A study coordinator will collect data at 30 days and at 1 year to document any complications or re-operations. Additionally, the study coordinator will assess whether the patient is having any swallowing complications following surgery.

8) Health resource utilization information (including out-of-pocket expenses) will be obtained using patient diaries along with copies of all medical bills and receipts at 1 month, 3 months, 6 months, and 12 months post-operatively for all of the patients. Participants also will be asked to keep track of days missed from work and days unable to perform usual activities, in addition to days missed from work for medical treatments or evaluations.

F. Data and Safety Monitoring Plan

- 1) All serious unexpected adverse events (e.g. death within 30 days of operation) will be reported to the IRB within 24 hours. Any appropriate funding agencies or regulatory agencies would be notified as well.
- 2) Any serious anticipated adverse event (e.g. wound infection, pulmonary embolus) will be reported to the IRB whenever their magnitude or frequency exceeds expectations.
- 3) All other adverse events (including loss of privacy, significant economic harm) will be reported to the IRB on an annual basis or at the time that re-approval is sought. Any adverse event judged unlikely or unrelated to the study will also be included in an annual report for the IRB.

G. Statistical Considerations

a. Specific data variables being collected for the study.

The data collection sheets will be submitted along with this protocol. There will be several data sheets as follows:

- 1) Screening/Baseline, 1 Month, 3 Months, 6 Months, and 1 Year Visit Checklist
- 2) Informed Consent Process
- 3) Inclusion/Exclusion Criteria
- 4) Baseline Demographics
- 5) Spine surgeon's data sheet

- 6) 30-day and 1 Year morbidity data sheet
- 7) 1 Month, 3 Months, 6 Months, 1 Year Return to Work Status
- 8) 3 Month Swallowing Evaluation

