The research team has extensive experience conducting economic evaluations, including assessment of musculoskeletal interventions alongside RCTs and will conduct the proposed patient-oriented health resource utilization analysis. We will collect health resource utilization data as well as health cost data alongside this RCT.

Cost Analysis

Costs will be estimated for each patient from a societal perspective from the sources listed below, including only patients from the United States. A one-year time horizon will be selected to align with the primary outcome measure of the CSM-S Trial.

A. Index Hospitalization Costs:

- Hospital Costs: Total hospital charges (TotalHC) will be used to estimate costs using hospital-specific and year-specific Medicare cost-to-charge ratios (CCR). The costs will be adjusted for inflation to the current year without a 3% discount.
 - As a sub-analysis, hospital charges for specific revenue-centers (i.e., radiology, pharmacy, physiotherapy and occupational therapy) will be converted to costs using hospital-specific and year-specific Medicare CCRs. This will allow the identification of the major drivers of the difference in cost between the surgical strategies. A crosswalk between the revenue center and the cost center will be created.
- For professional services (identified with either HCPCS code or CPT-4 codes) provided to patients during the index hospitalization, costs will be calculated using national reimbursement amounts from the appropriate Medicare fee schedules for the respective year and site.

B. One-Year All-Cause Costs:

- One-year total hospital charges will be utilized in this part of the analysis. These include major health resource utilization events in the year following surgery including readmission, reoperation, injections, advanced imaging, and physical therapy.
 - Year-specific, site-specific Medicare cost-to-charge ratios, will be used to determine one-year costs from charges. These costs will be inflation adjusted. Professional services will also be included (identified with either HCPCS code or CPT-4 codes) and costs will be calculated using national reimbursement amounts from the appropriate Medicare fee schedules for the respective year and site.

C. Costs Due to Lost Productivity:

- We will assume that work was halted for patients on the procedure date.

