- Lost wages will be estimated according to patients' occupations using the median weekly earnings in the US (for the current year) as reported by the Bureau of Labor Statistics.

- Lost wages for retirees will be valued at 65% of an employed patient and based on time to return to normal activities, which will be assumed to be three months

Hospitalization costs and one-year all-cause costs (total direct costs) will be combined with costs due to loss of productivity (indirect costs) to estimate total costs of each surgical procedure from a societal perspective.

Statistical Analysis Plan: The three cost outcomes will be reported in US Dollars and inflation-adjusted to the current year using the Gross Domestic Product Implicit Price Deflator. We will provide the descriptive statistics for the three outcomes (mean, median, standard deviation or SD, interquartile range, minimum, and maximum). Given that the cost outcomes are expected to follow a skewed distribution (non-normal), we will use generalized linear modeling (GLM) with Gamma distribution and a logarithmic link for cost. Any baseline patient characteristics found to be imbalanced between the cohorts will be adjusted for in the GLM. The mean predicted costs for each cohort and the differences in those predicted costs along with the 95% confidence intervals will be generated. If 10% or more of the overall study population has zero costs for the 1-year outcome, two-part modeling will be implemented. This will utilize a logistic regression to predict the presence of positive costs and a GLM model to predict non-zero costs as described above.

Calculation of Utility and Quality-Adjusted Life Years (QALY) Gained

- EQ-5D health-related quality-of-life questionnaires have been collected at baseline, 3 months, 6-months, 1-year, and 2-years. 1-year data will be used for cost-utility analyses.
 - For patients without complete data (i.e., without responses at all time points in the first year), we will assume missingness at random (MAR) and multiple imputation will be performed.
- Patient responses to the EQ-5D instrument will be mapped to utilities using the U.S. population value set and QALYs will be calculated for cost-utility analysis assuming a linear relationship between consecutive survey timepoints.

Incremental Cost-Effectiveness Ratio (ICER)

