- The ICER will be calculated in a three-way extended dominance analysis, comparing each surgical treatment to the others. If a surgical procedure is both less costly and provides higher QALYs gained, that treatment will be dominant

over the others.

- A comparison of anterior and posterior approaches (namely, grouping the two posterior procedures) will be performed independently from the ICER model.
- Probabilistic analysis will be performed to account for sampling variation around ICER point estimates.
- Cost/QALY gained will be reported for each surgical treatment and for each approach.

d. Power Analysis.

Sample size for Specific Aim #1a (Ventral surgery is associated with superior SF-36 PCS outcome at one year compared to dorsal (fusion or laminoplasty surgery):

Sample size estimates were calculated based on analysis of covariance model with $\alpha = 0.05$ at 80% and 90% power using Power Analysis and Sample Size software (PASS 2008, NCSS, LLC. Kaysville, Utah). The primary endpoint is the SF-36 PCS. This component of the SF-36 is derived from the sums of scores of 21 items and thus exhibits distributional behavior commensurate with assumptions for parametric analysis. Our preliminary data suggest standard deviations for SF-36 PCS between 10 and 12 and correlations of baseline with one year SF-36 PCS between 0.6 and 0.7. *The following table describes the total sample size (2:3 ventral-dorsal randomization) required to detect a five point difference in SF-36 PCS one year post-surgery for various combinations of power, standard deviation and one year correlations under a fixed design.*

A minimum sample size of **137** patients provides at least 90% power (see Tables below):

Surgery (N)	Pre-op	Post-Op	Correlation between Pre- and Post-Op	Difference
Ventral (45)	35.5 ± 10.3	44.2 ± 11.7	0.64	+ 8.7 ± 8.2
Dorsal (70)	35.8 ± 11.3	39.8 ± 11.6	0.66	+ 4.0 ± 9.5
Dorsal Fusion (42)	35.0 ± 11.7	39.6 ± 12.4	0.65	+ 4.6 ± 10.0
Laminoplasty (28)	37.0 ± 10.9	40.1 ± 10.6	0.67	+ 3.1 ± 8.8
All patients (115)	35.7 ± 10.9	41.5 ± 11.8	0.64	+ 5.8 ± 9.7

Difference / SD	Correlation	80% Power / 5% Type I error (2-sided)			90% Power / 5% Type I error (2-sided)		
		N _{Ventral}	N _{Dorsal}	N	N _{Ventral}	N _{Dorsal}	N

5 / SD = 10	0.60	38	56	94	50	74	124
5 / SD = 10	0.65	40	59	99	53	78	131
5 / SD = 10	0.70	42	62	104	55	82	137

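### Read as written, the QALY imputation rule covers patients who die in the first year and replaces a known utility of 0 with survivor-like values

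*Combined protocol and SAP*

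**What the plan says.** The relevant text is in Section II.G.c, under Calculation of Utility and Quality-Adjusted Life Years (QALY) Gained.

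- **Who is imputed.** "For patients without complete data (i.e., without responses at all time points in the first year), we will assume missingness at random (MAR) and multiple", thus prescribing imputation. The only criterion is an incomplete set of first-year responses.
- **Where utilities come from.** "Patient responses to the EQ-5D instrument will be mapped to utilities using the U.S. population value set". No other source of a utility value is named.
- **How QALYs are formed.** "QALYs will be calculated for cost-utility analysis assuming a linear relationship between consecutive survey timepoints". The first-year surveys are at baseline and 3, 6 and 12 months, and the cost analysis sets a one-year horizon.
- **How QALYs are used.** They feed the three-way ICER in the next subsection, where "If a surgical procedure is both less costly and provides higher QALYs gained, that treatment will be dominant" over the others.

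Elsewhere, the Data and Safety Monitoring Plan (Section II.F) names "death within 30 days of operation" as an example of a serious unexpected event, and the list of data sheets (Section II.G.a, item 21) includes a Death Form. Nowhere do the documents assign a utility to the dead state, end the QALY at death, or keep deaths out of the imputation. The sensitivity analyses for departures from MAR, under Statistical Methods, are described for the SF-36 PCS mixed model and not for the QALYs.

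**The concern.** A patient who dies at one month has no 3-, 6- or 12-month EQ-5D and so falls within the stated imputation set. There is no response to map, so the imputation rule is the only written route to a value. An imputation model is fitted to the responses of living patients, so the values it supplies for the dead are, on average, positive and survivor-like.

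A QALY combines length and quality of life, and time after death counts as 0. That value is known. MAR is an assumption about values that exist but were not observed, so it does not apply here.

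At stake is whether mortality counts at all in the effectiveness side of a comparison of operations in patients aged 45 to 80. Under the literal rule a first-year death costs its group almost nothing in QALYs. The group with the higher proportion of deaths therefore gains, relative to a correct calculation, and the ICER and the dominance rule inherit the error.

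**Working it through.** **Inputs from the documents.** The Power Analysis inflates 137 patients by 5% and then by 10%: 137 × 1.05 × 1.10 = 158.2, rounded up to 159, which reproduces the stated total. At 2:3 allocation, 159 × 0.4 = 63.6 and 159 × 0.6 = 95.4, so about 64 ventral and 95 dorsal. The documents give no utility, QALY or mortality figure to reproduce.

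**Assumptions.** A survivor accrues u = 0.6 to 0.8 QALY in year 1. Utility before death is about 85% of that level.

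**Overstatement per death at day d** = u − 0.85 × u × d/365.

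| u | Day 30 | Day 182 |
|---|---|---|
| 0.6 | 0.558 | 0.346 |
| 0.7 | 0.651 | 0.403 |
| 0.8 | 0.744 | 0.461 |

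**Shift in the arm mean per day-30 death** = overstatement / n.

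- Ventral: 0.558/64 = 0.009 to 0.744/64 = 0.012.
- Dorsal: 0.558/95 = 0.006 to 0.744/95 = 0.008.

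**Cross-check with utility paths.** Assume utilities of 0.60, 0.70, 0.75 and 0.75 at 0, 3, 6 and 12 months. The trapezoid weights are 0.125, 0.25, 0.375 and 0.25, so the full year gives 0.075 + 0.175 + 0.281 + 0.188 = 0.719 QALY. For a death at month 1, utility has reached 0.633 and the area to death is (0.600 + 0.633)/2 × 1/12 = 0.051. The excess is 0.719 − 0.051 = 0.667 (before rounding), or 0.0104 per death in 64 and 0.0070 in 95. The excess is 0.497 for a death at month 4 and 0.188 at month 9. For month-1 deaths, a lower path (0.50 rising to 0.60) and a higher path (0.70 rising to 0.85) give 0.0083 to 0.0119 in 64 and 0.0056 to 0.0080 in 95, in line with the first calculation.

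**Entering 0 at the next survey is not enough.** With a month-1 death and 0 entered at month 3, linear interpolation gives 0.5 × 0.60 × 0.25 = 0.075 QALY, against 0.051 when accrual stops at death.

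**Direction.** A simulation used equal true utilities in both arms (SD 0.2 and correlation 0.65, both assumed), month-1 deaths, and within-arm regression imputation (2,000 replicates, 10 imputations). The table shows the dorsal-minus-ventral QALY difference.

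| Deaths ventral/dorsal | Rule as written | Utility 0 after death |
|---|---|---|
| 0/0 | 0.000 | 0.000 |
| 0/2 | 0.000 | −0.014 |
| 2/0 | +0.001 | +0.022 |
| 1/1 | −0.001 | +0.003 |

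The rule pulls the difference back to about zero. It removes the penalty for death. With one death in each arm, the bias of about 0.003 is toward ventral, where one death is the larger proportion.

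**The case against.** The strongest reply is that the bullet is about questionnaire non-response. It never mentions death, and a health economist would enter 0 for the dead without being told. It is true that the plan does not say in words that deaths will be imputed. But the imputation set is defined by one criterion that deaths satisfy, nothing exempts them, and even the informal practice of entering 0 leaves the interpolation error shown above. The reply therefore limits how certain one can be about what the analyst will do. It does not mean that the text already handles death.

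On size, the reply has force. The utilities are assumed and the documents give no number of deaths. Costing is restricted to patients in the United States and the ICER compares three procedures, so 64 and 95 need not be the analysed numbers. With a QALY SD of 0.15 to 0.25 (assumption), the standard error of a 64-versus-95 difference is SD × √(1/64 + 1/95) = 0.024 to 0.040. One excess early ventral death, at 0.0104, is then about 0.26 to 0.43 of a standard error.

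A reader might also infer several stronger things that the documents do not support:

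- **That a group with deaths looks cheaper than it is.** Charges do end at death, index hospitalization costs are still counted, and no section imputes costs.
- **That the arm with more deaths must come out ahead.** The bias follows the proportion. Four ventral deaths in 64 (6.3%) against five dorsal in 95 (5.3%) biases toward ventral, the arm with fewer deaths.
- **That the plan expects deaths.** Its example is listed among unexpected events; the Death Form shows only that deaths can be recorded.

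**Conclusion.** The concern holds for the QALYs. As written, the rule sends first-year deaths to multiple imputation under MAR and replaces a known 0 with survivor-like utility. The resulting bias runs toward the group with the higher death proportion.

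The size of 0.56 to 0.74 QALY per day-30 death rests on the assumed 0.6 to 0.8 QALY per survivor-year and the 85% factor. The 0.006 to 0.012 shift in an arm mean further assumes that all randomized patients are analysed; it scales inversely with group size, so it would be larger in smaller procedure groups. Later deaths matter less, and with no deaths the bias is nil.

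The effect is confined to the cost-utility analysis, the ICER and the dominance rule. The primary SF-36 PCS comparison is untouched. A reader might want to convert the shift into dollars per QALY, but the documents give neither a cost difference nor a QALY difference, so any such figure would be invented.

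**What to change.** In the QALY subsection of Section II.G.c, add that multiple imputation applies only to time points at which the patient was alive, that utility is 0 from the date of death, and that QALYs accrue up to that date instead of being interpolated to the next survey. The same sentence should say which utility applies between the last survey and death.

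This is a change to the analysis text only. If the Death Form records the date of death, which is likely although its contents are not shown, no new data are needed. The downside is that QALYs in a group with deaths become slightly lower and more variable.

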- 9) Initial Hospital Admission Data Sheet
- 10) 3 Months and 1 Year Radiology
- 11) End of Study
- 12) Adverse Event Form
- 13) Serious Adverse Event Report Form
- 14) Serious Adverse Event Follow-up Report Form
- 15) SF-36 questionnaires (pre-op, 3 months, 6 months, 1, 2, 3, 4, and 5 years),
- 16) Neck Disability Index questionnaires (pre-op, 3 months, 6 months, 1, 2, 3, 4, and 5 years)
- 17) mJOA, (pre-op, 3 months, 6 months, and 1 year)
- 18) EuroQol-5D (pre-op, 3 months, 6 months, 1, 2, 3, 4, and 5 years)
- 19) Health Resource Utilization Diary (1 month, 3 months, 6 months, 1 year)
- 20) Report of Second Cervical Surgery
- 21) Death Form
- 22) Inpatient Hospital and Rehabilitation Utilization Data Sheet
- 23) Long term follow-up phone questionnaire (2, 3, 4, and 5 years)

b. Study endpoints.

Subjects will be followed for 5 years. The primary endpoint will be the 1-year change in SF-36 physical component summary score (PCS) at one year. Secondary endpoints will include the 1-year change in mJOA, NDI, and EuroQol-5D scores as well as the observed complication rates, health service utilization, work status, and sagittal balance measurements.

c. Statistical Methods.

Primary analyses will include all subjects randomized using an intent-to-treat approach. The primary endpoint is the 1-year change in Physical Component Summary of the SF-36 (SF-36 PCS) at one year. A likelihood-based analysis using a mixed model will be used to compare SF-36 PCS between groups. This model will adjust for baseline SF-36 PCS, as well as study surgeon using a random effects model. All time points will be included in the model, and each subject will contribute data for the time points at which they were assessed. The model enables a statistical comparison between treatment groups at each time point, though the comparison at the one-year time point will be the primary analysis. The primary advantage of the mixed model, when compared to commonly used methods such as complete case analysis and single imputation (e.g. last observation carried forward), is its flexibility in handling missing data. This analysis will assume that missing data occurs at random (i.e. the missing data value can be dependent on observed data, but independent of unobserved

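### No baseline EQ-5D adjustment is specified for the QALY difference, although the cost model adjusts for any baseline imbalance found, so the ICER may mix the two

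*Combined protocol and SAP*

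**What the plan says.** All places are in the combined protocol and SAP, section II.G.

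- **Costs** (Analysis Plan for Cost-Effectiveness, statistical paragraph of the Cost Analysis): "we will use generalized linear modeling (GLM) with Gamma distribution and a logarithmic link for cost", and "Any baseline patient characteristics found to be imbalanced between the cohorts will be adjusted for in the GLM".
- **QALYs** (Calculation of Utility and QALY Gained): EQ-5D responses are mapped with the US value set, missing first-year responses are multiply imputed under MAR, and "QALYs will be calculated for cost-utility analysis assuming a linear relationship between consecutive survey timepoints". No comparison model or covariate follows.
- **ICER**: "The ICER will be calculated in a three-way extended dominance analysis, comparing each surgical treatment to the others". Anterior versus posterior is compared separately. "Cost/QALY gained will be reported for each surgical treatment and for each approach". "Probabilistic analysis will be performed to account for sampling variation around ICER point estimates". No QALY covariate is added here either.
- **Primary outcome** (Statistical Methods): "This model will adjust for baseline SF-36 PCS, as well as study surgeon using a random effects model".
- **Randomisation** (Power Analysis; Analysis Plan for Year 2 Outcomes): ventral versus dorsal in a 2:3 ratio, giving two randomised groups. No randomisation between dorsal fusion and laminoplasty is described.

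**The concern.** Baseline utility affects a patient's one-year QALY in two ways: as the first point of the area, and through its correlation with later scores. If the groups differ at baseline, by chance or by selection, part of that gap appears in the QALY difference unless the comparison adjusts for it. Subtracting baseline does not solve this. It over-corrects and reverses the sign of what carries over.

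The plan provides for adjustment on the cost side only. When that adjustment is triggered, the numerator of the ICER may be adjusted while the denominator is not. The consequences differ by contrast:

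- **Ventral versus dorsal, as randomised:** lost precision, and chance imbalance left in the estimate. Both pass into the probabilistic analysis.
- **Contrasts that take fusion and laminoplasty separately:** baseline differences need not be chance, so confounding is possible as well.

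**Working it through.** The documents give no EQ-5D SD, correlation, baseline gap, QALY or ICER, so there is no stated figure to reproduce. The sizes below rest on labelled assumptions.

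**Inputs**

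- Time points 0, 0.25, 0.5 and 1 year, and a one-year horizon (Analysis Plan for Cost-Effectiveness).
- Correlation r = 0.60 to 0.70, borrowed from the Power Analysis ("correlations of baseline with one year SF-36 PCS between 0.6 and 0.7"). Using it for EQ-5D is an assumption.
- Baseline SD = 1. Follow-up SD = k, with k = 1 or 1.2 (assumed). All pairs of time points share the same r.

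**Step 1: trapezoid weights.** Baseline 0.25/2 = 0.125; 3 months (0.25 + 0.25)/2 = 0.25; 6 months (0.25 + 0.5)/2 = 0.375; 12 months 0.5/2 = 0.25. They sum to 1.

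**Step 2: share of a baseline gap that carries over.** Raw area: s = 0.125 + 0.875kr. Area minus baseline: s - 1.

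**Step 3: variance.** After adjustment for baseline, under either definition, V = k²(0.265625 + 0.5r - 0.765625r²). Here 0.265625 is the sum of the squared follow-up weights, 0.765625 = 0.875², and 0.5 is their difference. Without adjustment the variance is V + s² (raw) or V + (s - 1)² (subtracted). The SE cut is 1 - √(V / unadjusted variance).

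| k | r | V | s | Raw variance | SE cut, raw | Subtracted variance | SE cut, subtracted |
|---|---|---|---|---|---|---|---|
| 1 | 0.60 | 0.2900 | 0.6500 | 0.7125 | 36.2% | 0.4125 | 16.2% |
| 1 | 0.70 | 0.2405 | 0.7375 | 0.7844 | 44.6% | 0.3094 | 11.8% |
| 1.2 | 0.60 | 0.4176 | 0.7550 | 0.9876 | 35.0% | 0.4776 | 6.5% |
| 1.2 | 0.70 | 0.3463 | 0.8600 | 1.0859 | 43.5% | 0.3659 | 2.7% |

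Example, first row: 1 - √(0.2900/0.7125) = 36.2%.

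A simulation with k = 1 and the protocol's expected 55 and 82 patients (20,000 runs) gave cuts of 35.9% and 16.4% at r = 0.60, and 45.3% and 11.8% at r = 0.70. The percentages do not depend on the sample size.

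**Step 4: sensitivity, k = 1.**

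- If follow-up scores correlate 0.8 with each other and 0.60 to 0.70 with baseline, the cut is 31-41% (raw) or 10-13% (subtracted).
- If the common r is only 0.3, it is 16.5% (raw) or 30.7% (subtracted).

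**Step 5: non-randomised contrasts.** With an assumed slope b of follow-up on baseline utility, a baseline gap of 0.01 shifts the unadjusted difference by 0.01(0.125 + 0.875b) for raw area, or by -0.00875(1 - b) if baseline is subtracted. For b = 0.3 to 0.7 that is +0.0039 to +0.0074 QALY, or -0.0061 to -0.0026 QALY. The true gap is unknown. The preliminary data in the Power Analysis show pre-operative PCS of 35.0 for fusion and 37.0 for laminoplasty, or 2.0/10.9 = 0.18 SD. That is a different instrument in pilot patients and only suggests that the two groups can differ.

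**The case against.** The strongest replies, and what stands of each:

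- **The plan is silent; it does not choose an unadjusted analysis.** This stands. A reader might infer that the sponsor decided against adjustment, or that the ICER definitely divides an adjusted cost difference by an unadjusted QALY difference. The text supports neither. Cost adjustment applies only if imbalance is found, and the ICER section does not say that it uses the model-predicted costs. The mismatch is possible, not certain.
- **The plan's own practice is mixed.** This stands. The Year 2 models analyse change from baseline without baseline adjustment, so the primary model is a precedent and not a uniform rule.
- **Baseline variables are described as similar between groups.** That remark justifies the Year 2 models, and it is the only statement on imbalance. Those models also cover the as-treated groups, so it may suggest a small gap. It gives no EQ-5D figures, and similar groups do not remove the precision gain.
- **The large percentages need the raw-area reading.** This stands. QALY gained is not defined, and if it means area minus baseline the gain is modest. With the preliminary all-patient PCS SDs as a ratio (k = 11.8/10.9 = 1.083), the cut is 7-12%.
- **Primary endpoint.** The primary SF-36 PCS result is untouched. This stands too.

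**Conclusion.** The point holds as a gap in the economic analysis plan that is worth closing. No baseline EQ-5D adjustment is specified for the QALY difference, while the cost model has a conditional one.

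For ventral versus dorsal, compared by randomised assignment, the issue is precision. At assumed correlations of 0.60 to 0.70, equal across time points, adjustment cuts the SE by about 36-45% (raw area; 35-44% with follow-up SDs 20% larger) or about 3-16% (baseline subtracted, across the two follow-up SDs). Other correlation patterns move these figures, as shown in the working.

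For contrasts that separate fusion from laminoplasty, confounding of the denominator is possible, but its size cannot be stated.

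Three stronger readings are not supported:

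- **That the randomised QALY difference is biased.** It is not; chance imbalance affects precision.
- **That the percentages apply to the ICER or to the three-way analysis.** They concern the randomised QALY difference only.
- **That non-randomised patients are certain to enter.** The economic section limits patients to the United States and describes data collection alongside the RCT, while section II.E item 8 collects resource use on everyone. The question is open and secondary here.

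**What to change.** Add to the Analysis Plan for Cost-Effectiveness:

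1. Estimate QALY differences by regression on treatment group with baseline EQ-5D utility as a covariate, within the planned multiple imputation, for both the three-way and the ventral-versus-dorsal comparisons. The adjusted group difference is the same whether QALYs are raw area or area minus baseline, because subtracting the covariate changes only its own coefficient. This also removes the ambiguity in QALY gained for the between-group comparison.
2. Use the same pre-specified baseline covariates, including baseline EQ-5D, in the cost and QALY models, in place of selection by observed imbalance.
3. Carry the adjusted cost and QALY differences into the ICERs and the probabilistic analysis.
4. Report the three-way comparison as non-randomised, and state that adjustment addresses measured baseline differences only.

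The cost is a few sentences of SAP text and a few regressions. Baseline EQ-5D is already collected. The covariates should be fixed before the cost-utility analysis is run; the documents do not say whether it has been.

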The sample size will be inflated by 5% to accommodate multiple significance testing using an O'Brien-Fleming stopping boundary. Based on our preliminary data and pilot studies, withdrawal and loss-to-follow-up are not expected to be high. The sample size will be further inflated by 10% to accommodate attrition during the follow-up. Thus, 159 total patients will be recruited and randomized. **Ten high volume surgeons/ centers with the necessary expertise to permit patient randomization (16 randomized CSM cases/ site) have been selected to achieve the goal of enrolling 159 randomized patients over 18 months. An additional 91 nonrandomized patients will be enrolled into the study.**

Sample size for Specific Aim #1b (Compared to pre-operative baseline status, both ventral and dorsal surgery for CSM improve symptoms of spinal cord dysfunction at one year follow-up):

Using the sample size estimate for Specific Aim #1a and assuming ~10% attrition during follow-up, we expect to have 55 ventral surgery and 82 dorsal surgery patients (total = 137 patients) available for analysis. We will be able to detect changes from baseline pre-operative mJOA status as small as 2.0 points (clinically important difference) for both the ventral surgery cohort and the dorsal surgery cohorts at one year. Assumptions for this sample size analysis include Type I alpha = 0.025, power at 90%, and range of within-subject correlation of 0.60 to 0.70.

H. Economic Considerations

No subject will incur any additional cost for participating in this study. All of the pre- and post-operative CT, MRI, flexion-extension x-rays, and pre-operative sagittal balance films are considered standard of care. The post-operative sagittal balance films, which only randomized patients will receive, are not considered standard of care and will be billed directly to the research fund. All costs associated with the administration of the study will be assumed by the Patient-Centered Outcomes Research Institute (PCORI) and/or the Lahey Comparative Effectiveness Research Institute.

[figure not shown]
III. HUMAN SUBJECTS

A. Subject Population, Recruitment

Eligibility Criteria: Patients aged 45-80 years with CSM (≥ 2 levels of spinal cord compression from C3 to C7) presenting with ≥ 2 of the following symptoms/signs: clumsy hands, gait disturbance, hyperreflexia, up going toes, bladder dysfunction.

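### The Aim 1a sample-size table does not follow from the ANCOVA it names, and the 90% power claim for 137 patients rests on the lowest planning SD

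*Combined protocol and SAP*

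**What the plan says.** All of this is in section II.G.d, Power Analysis, of the combined protocol and SAP.

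- **Method:** "Sample size estimates were calculated based on analysis of covariance model", with a two-sided alpha of 0.05, 80% and 90% power, and 2:3 ventral-to-dorsal allocation. The table gives the total "required to detect a five point difference in SF-36 PCS one year post-surgery".
- **Inputs:** "Our preliminary data suggest standard deviations for SF-36 PCS between 10 and 12", with correlations from 0.6 to 0.7. The pilot table gives within-arm post-operative SDs of 11.7 (ventral, n = 45, correlation 0.64) and 11.6 (dorsal, n = 70, correlation 0.66).
- **Table:** it is announced as covering "combinations of power, standard deviation and one year correlations under a fixed design". Every row that can be read has SD = 10. For correlations 0.60/0.65/0.70 the totals are 94/99/104 (80% power) and 124/131/137 (90% power).
- **Conclusion:** 137 "patients provides at least 90% power (see Tables below". This total is then inflated by 5% for O'Brien-Fleming testing and by 10% for attrition, giving 159 to be randomised. Aim 1b uses it again: "we expect to have 55 ventral surgery and 82 dorsal surgery patients (total = 137 patients) available for analysis".

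**The concern.** A baseline covariate removes the share of variance it explains. The stronger the correlation, the smaller the residual variance and the fewer patients an ANCOVA needs. The printed totals go the other way in both power blocks, so they cannot come from the named model.

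A separate problem is that the text offers SDs of 10 to 12 but takes 137 from a row at the bottom of that range, while both pilot arms sit near the top. The sentence about 90% power carries no such condition.

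What is at stake is whether a reader can reproduce the planning figures and know what power the trial was designed to have. The figure of 137 underlies the 159 to be randomised and the Aim 1b calculation.

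**Working it through.** **1. The plan's own figures.** Each total is the sum of its printed arms (50 + 74 = 124, 53 + 78 = 131, 55 + 82 = 137; 38 + 56 = 94, 40 + 59 = 99, 42 + 62 = 104), so the rising pattern is not a garbled digit. The inflation also reproduces: 137 × 1.05 = 143.85, taken as 144; 144 × 1.10 = 158.4, taken as 159.

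**2. ANCOVA sample size.** Residual variance is SD² × (1 − ρ²). The normal approximation with a 2:3 split is

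N = (1.960 + z_power)² × SD² × (1 − ρ²) / 5² × (1/0.4 + 1/0.6).

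For SD 10, ρ = 0.70 and 90% power: (1.960 + 1.282)² × 51/25 × 4.167 ≈ 89. The exact noncentral-t calculation (df = N − 3) gives 92 as the smallest total, or 93 if the dorsal arm is 1.5 times the ventral arm rounded up. The plan prints 137.

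| SD 10 | ρ = 0.60 | ρ = 0.65 | ρ = 0.70 |
|---|---|---|---|
| Printed, 80% power | 94 | 99 | 104 |
| ANCOVA, 80% power (rounded-arm totals) | 88 | 78 | 70 |
| Printed, 90% power | 124 | 131 | 137 |
| ANCOVA, 90% power (rounded-arm totals) | 115 | 105 | 93 |

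ANCOVA power at the printed sizes is 83.7/88.9/93.4% in the 80% block and 92.3/95.6/97.9% in the 90% block.

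**3. Could another formula explain the table?** By normal approximation at 90% power and SD 10, a one-sided ANCOVA gives 91/82/73, an unadjusted t-test 175 in every row, and a change score 140/123/105. None fits. The mean of four equally correlated measurements, with variance factor (1 + 3ρ)/4, fits closely: power at the printed sizes is 80.3–80.4% and 89.9–90.1%. The plan does not name that formula, and a mean of five comes near (81.1–81.5% and 90.4–90.8%), so this source is only an inference. It would also not match the primary comparison, which is at one year.

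**4. ANCOVA power with 137 patients (55/82).** Example at SD 12, ρ = 0.60: residual SD = 12 × √(1 − 0.36) = 9.6; standard error = 9.6 × √(1/55 + 1/82) = 1.673; noncentrality = 5/1.673 = 2.99; power 84.3%.

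| SD | ρ = 0.60 | ρ = 0.65 | ρ = 0.70 |
|---|---|---|---|
| 10 | 94.5% | 96.3% | 97.9% |
| 11 | 89.9% | 92.6% | 95.2% |
| 12 | 84.3% | 87.8% | 91.4% |

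The largest SD that keeps 90% power is 10.98, 11.56 and 12.30 for the three correlations.

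**5. At the pilot values.** Pooled within-arm SD = √[(44 × 11.7² + 69 × 11.6²)/113] = 11.64. Power is 89.0% at ρ = 0.64 and 90.3% at ρ = 0.66. With each arm's own correlation the pooled residual SD is 8.82 and power is 89.8%. The all-patients SD of 11.8 is not used because it includes the difference between arms.

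One sensitivity: the ventral pilot row is not self-consistent. Its change SD of 8.2 implies a correlation of (10.3² + 11.7² − 8.2²)/(2 × 10.3 × 11.7) = 0.73, whereas the printed 0.64 implies a change SD of 9.4. Taking the printed change SDs instead gives a residual SD of 8.47 and power of 92.0%.

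**6. If attrition is exactly 10%.** 159 × 0.9 ≈ 143 evaluable (57/86). Ignoring any sequential penalty, SD 12 gives 85.7/89.0/92.4%, and SD 11 with ρ = 0.60 gives 91.0%.

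**The case against.** The strongest reply is that the power sentence points to the tables, and 137 is the largest total shown there. Under ANCOVA it gives well over 90% in every SD = 10 row, and at the pilot values it gives about 90%. The error in the table makes N too large, and that slack absorbs most of the effect of a larger SD. All of this is true, and it is why the trial should not be called badly underpowered. It does not rescue the sentence, which states no SD while the text around it gives a range up to 12.

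Three smaller points also deserve weight.

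- The SD 11, ρ = 0.60 cell misses by only 0.1 point, and a normal approximation puts it at 90.3%. The real shortfall is therefore the two SD 12 cells.
- Rows for SD 11 or 12 may have been lost when the PDF was read. That would not change the direction of N within the SD = 10 rows, nor the fact that 137 is an SD = 10 figure.
- This is version 6.0, and its Year 2 section refers to year 1 analyses already done, so the correction cannot alter recruitment. It remains a correction of figures on which the plan relies.

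**Conclusion.** Both faults hold. The table contradicts the named method in direction. At SD 10, ρ = 0.70 and 90% power it prints 137 where ANCOVA needs 92 to 93. The claim of at least 90% power fails over part of the plan's own range: 137 evaluable patients give about 84% to 98%, and about 89% to 90% at the pilot within-arm SD and correlations of 0.64 to 0.66. The shortfall is confined to the upper SDs with the lower correlations.

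These figures assume a 5-point difference, two-sided alpha of 0.05, a 55/82 split and a fixed design. They leave out the random surgeon effect in the planned mixed model and the cost of interim looks, for which the plan adds 5% separately. Where the printed numbers came from remains unknown.

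**What to change.** Replace the table with ANCOVA totals over the stated ranges. For 90% power, with the dorsal arm set to 1.5 times the ventral arm and rounded up:

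| SD | ρ = 0.60 | ρ = 0.65 | ρ = 0.70 |
|---|---|---|---|
| 10 | 115 | 105 | 93 |
| 11 | 138 | 125 | 113 |
| 12 | 165 | 148 | 133 |

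Taking the smallest total instead lowers some entries by one or two. The 80% block should be recalculated in the same way.

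Reword the power sentence along these lines:

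> With 137 evaluable patients (55 ventral, 82 dorsal), fixed-design ANCOVA power for a 5-point difference is about 84% to 98% over SDs of 10 to 12 and correlations of 0.60 to 0.70, and about 90% (89–90%) at the pilot within-arm SD of 11.6 and correlations of 0.64 to 0.66, before inflation for O'Brien-Fleming testing and attrition.

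The cost is one recalculated table and one sentence. The stated power becomes slightly less favourable at the upper SDs. Enrolment does not need to change, and a short note can keep the record of how 159 was reached.
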